Testing Ultraprocessed Front-of-Package Labels in Chile

NCT06293963

April 10th, 2025

Study Protocol and Analytic Plan

Introduction

This study aims to examine the effects of a warning label signaling that a product is ultraprocessed among a sample of Chilean parents. This document pre-specifies our planned analytic approach prior to data collection.

Study Protocol

Participants will complete an online randomized experiment programmed in Qualtrics. After providing informed consent and completing a parent study, participants will be randomly assigned into 1 of 2 arms: a control arm or an ultraprocessed warning label arm. In the control arm, products will carry only nutrient warning labels per Chile's current policy, while in the ultraprocessed warning label arm, products will carry both nutrient labels and an ultraprocessed warning label.

Participants will see three different mock bags of potato chips with the same flavor (designed to mitigate confounding by product type or flavor) displayed in a random order. All three products will be ultraprocessed. One product will not be high in any nutrients of concern, one will be high in sodium, and one will be high in sodium and saturated fat. For each product, participants will rate their purchase intentions, perceived product healthfulness, and indicate whether they believe the product to be ultraprocessed.

Hypotheses

Correct identification of UPFs (co-primary outcome): We predict that, compared to the control arm, correct identification of products as UPFs will be higher among participants in the UPF warning label arm (H1).

Purchase intentions (co-primary outcome): We predict that, compared the control arm, product purchase intentions will be lower among participants in the UPF warning label arm (H2).

Perceived product healthfulness (secondary outcome): We predict that, compared the control arm, perceived product healthfulness will be lower among participants in the UPF warning label arm (H3).

Moderation hypotheses: We predict that the impact of the UPF label on purchase intentions (H4) and perceived product healthfulness (H5) will be greater for the product not high in any nutrients of concern than for the products high in one or two nutrients of concern.

Main Analyses

We will use a two-sided critical alpha of 0.05 to conduct all statistical tests. All confidence intervals presented will use a 95% confidence level. Analyses of the primary

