For purchase intentions and perceived healthfulness (continuous outcomes), we will first descriptively report unadjusted mean scores for each product and averaged across products in each experimental arm. To test H2 and H3, we will use linear mixed-effects regression models. Models will include random intercepts to account for repeated measures within participants. Models will regress each outcome on indicator variables for experimental arm, indicator variables for product, and their interactions. After model estimation, we will test the joint statistical significance of the interaction terms. If the interactions are jointly significant, we will keep them in the model and report the average differential effect (ADE) of the UPF label (i.e., differences in predicted means between experimental arms) for each product. Alternatively, if the interactions are not jointly significant, we will drop them from the models and report the ADE of the UPF label across products. We will use complete case analysis to handle any missing data.

Sample Size and Power

This study will occur in a survey that will follow a parent experiment. The total sample of 3,300 size was calculated based on the primary outcomes of the parent study. Using G*Power3.1, we determined that the minimum effect size we would be able to detect with this pre-determined sample size. With an alpha of 0.05, 80% power, and 1 degree of freedom, we would be able to detect an effect of $d=0.06$ or larger. We concluded that this sample size would be enough, given that, on a previous study using similar labels, we found an effect size of $d=0.16$ on correct identification of products as UPF.

Exclusions and Outliers

We will exclude participants who complete the survey implausibly quickly (defined as $<1/3$ of the median completion time) and those who completed less than 90% of the survey.

Interim Analyses

No interim analyses are planned.

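### The plan shows N = 3,300 to be enough only for correct identification (H1); for co-primary purchase intentions (H2) the stated d = 0.06 is not reached unless a participant's three ratings are nearly uncorrelated

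*Combined protocol and SAP*

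**What the plan says.** Under Sample Size and Power, the size comes from another study: "The total sample of 3,300 size was calculated based on the primary outcomes of the parent study". The plan then works backwards to a detectable effect at alpha 0.05, 80% power and 1 df: "we would be able to detect an effect of $d=0.06$ or larger". It names no outcome, G*Power test family or within-participant correlation for that figure. The adequacy conclusion follows at once, with d = 0.16 for correct identification as its benchmark: "We concluded that this sample size would be enough, given that, on a previous study using similar labels, we found an effect size of".

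Hypotheses lists a second co-primary outcome, H2: "Purchase intentions (co-primary outcome): We predict that, compared the control arm, product purchase intentions will be lower among participants in the UPF warning label arm". The secondary outcome is perceived healthfulness (H3). H4 and H5 predict that the label's effect on these two outcomes "will be greater for the product not high in any nutrients of concern than for the products high in one or two nutrients of concern". No expected or smallest relevant effect is given for H2 or H3, and no power statement for H4 or H5.

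Under Main Analyses, each continuous outcome is fitted with a random-intercept linear model on arm, product and their interactions: "After model estimation, we will test the joint statistical significance of the interaction terms". If the interactions are significant, the label effect is reported for each product; if not, they are dropped and one pooled effect is reported. On significance level: "We will use a two-sided critical alpha of 0.05 to conduct all statistical tests".

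**The concern.** A detectable effect shows that a sample is large enough only when it is compared with an effect worth finding. The plan makes that comparison for H1 alone. Identification is also the outcome closest to the intervention, because the label tells participants the answer. Its effect size is no guide to how far the label shifts purchase intentions.

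The 0.06 is the only sensitivity figure in the plan, so a reader will apply it to H2 as well. If the true sensitivity for H2 is poorer, a null result on a co-primary outcome would be taken as coming from a study able to find effects of 0.06, when it could reliably find only larger ones.

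**Working it through.** **Inputs from the documents.** N = 3,300; two arms; three products rated by each participant; two-sided alpha 0.05; 80% power; 1 df; prior effect d = 0.16 on H1.

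**Assumptions, not in the documents.** Allocation is 1:1 (1,650 per arm). Effects are in SD units of a single rating. The three ratings have equal correlation r, which is the structure a random-intercept model implies. The values r = 0.3, 0.5 and 0.7 are illustrative.

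**Step 1: the plan's own figure.** For one rating per participant, the standard error of the arm difference is 2/√3,300 = 0.0348. The detectable effect is (1.960 + 0.842) × 0.0348 = 0.098, not 0.06. At d = 0.06 the power is 41%, and 80% power would need 4,361 per arm (8,722 in total). Other readings give:
- one-sided test: 0.087
- 3,300 per arm: 0.069
- Cohen's f or w with 1 df: 0.049
- 3 × 3,300 = 9,900 ratings treated as independent: 2.802 × 2/√9,900 = 0.056, which rounds to 0.06

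Of these, only the last rounds to the stated figure. The plan does not say which calculation was run.

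**Step 2: H1.** At d = 0.16 with 1,650 per arm, 0.16/0.0348 = 4.60, and Φ(4.60 − 1.96) gives 99.6% power.

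**Step 3: pooled arm effect on H2 (interactions dropped).** The variance is (4/N)(1 + 2r)/3, so the detectable effect is 0.0975 × √((1 + 2r)/3). Power at 0.06 is Φ(0.06/SE − 1.960).

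| r | SE | Detectable at 80% | Power at 0.06 |
|---|---|---|---|
| 0.3 | 0.0254 | 0.071 | 66% |
| 0.5 | 0.0284 | 0.080 | 56% |
| 0.7 | 0.0311 | 0.087 | 49% |

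Setting the detectable effect to 0.06: (0.06/0.0975)² = 0.378, and r = (3 × 0.378 − 1)/2 ≈ 0.07. If 0.06 is allowed to be a rounding of anything up to 0.065, r must still be below about 0.17. A larger r makes the pooled figure worse (0.091 at r = 0.8).

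**Step 4: one product (interactions kept).** The variance is 4/N whatever r is, so the detectable effect is 0.098 and power at 0.06 is 41%.

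**Step 5: losses.** Exclusions and Outliers removes very fast and incomplete respondents, and no rate is given. If 10% are lost (N = 2,970), each detectable effect rises by √(3,300/2,970) = 1.054: 0.075, 0.084 and 0.092 pooled, and 0.103 per product.

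**Step 6: joint arm-by-product test, for reference.** Two arms by three products gives (2 − 1)(3 − 1) = 2 interaction terms. The noncentrality needed for 80% power is 9.635 with 2 df, against 7.849 with 1 df. Let the label effect on the product with no nutrients of concern differ by D from an equal effect on the other two. The detectable D is then √9.635 × 0.0348 × √(1.5(1 − r)): 0.111, 0.094 and 0.072 at r = 0.3, 0.5 and 0.7, and 0.059 at r = 0.8. It equals 0.06 at r ≈ 0.79.

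**The case against.** The strongest defence is that N was fixed elsewhere, so this is a sensitivity statement and not a sample-size justification. The 0.06 names no outcome and can be read as covering the arm effect on either co-primary outcome. That stands in part: it would be too much to say that the plan offers nothing for H2. But if 0.06 is meant to cover H2, it has to be right for H2, and Steps 3 and 4 show that it holds only with nearly uncorrelated ratings. These are ratings by one person of three same-flavour bags of chips, so near-zero correlation would need a justification that the plan does not give.

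A second defence is that every H2 figure here depends on an unreported r. That is true of the exact value. But from r = 0 to r = 1 the pooled detectable effect runs from 0.056 to 0.098, and only the lowest end of that range supports 0.06.

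A reader might also infer that the plan claims 0.06 for the moderation hypotheses and that the 2-df test refutes it. The documents do not support this. The plan ties 0.06 to 1 df, never applies it to a difference between label effects, and introduces the interaction models as tests of H2 and H3. It does not say which test decides H4 and H5, and a 1-df contrast would fit their wording. Nor does the joint test always need larger effects: its detectable difference falls below 0.06 above r ≈ 0.79, and below the pooled figure at the same r above about 0.60. The plan also does not say that a non-significant interaction will be read as equal label effects, and it reports unadjusted means for each product in any case.

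**Conclusion.** The point holds for the adequacy sentence and for the 0.06 as applied to H2. The sample is ample for H1 at the cited effect. For H2 the detectable pooled effect is about 0.07 to 0.09 SD for r between 0.3 and 0.7, and about 0.10 SD per product. That is roughly 1.2 to 1.6 times the stated figure (0.071/0.06 to 0.098/0.06), before any exclusions. The same figures apply to H3, which uses the same model. They rest on 1:1 allocation, equal correlation between ratings and full retention of 3,300.

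It would go too far to conclude that the study is underpowered for H2. No expected H2 effect is given, so that cannot be judged either way. The absence of a power figure for H4 and H5 is missing detail, not a contradiction.

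**What to change.** In Sample Size and Power:

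1. Limit the adequacy sentence to H1, the only outcome with a cited prior effect.
2. Replace the single 0.06 with detectable effects for H2 and H3: about 0.07 to 0.09 SD for the pooled arm effect and about 0.10 SD for a single product. State the assumed within-participant correlation (from the previous study if available, otherwise a range such as 0.3 to 0.7), the G*Power test used, and the N expected after exclusions.
3. If a purchase-intention effect can be justified, give it and compare it with these figures. If not, say that none is available.
4. If a figure is added for the joint arm-by-product test, state it as conditional on r: a difference in label effects of about 0.11, 0.094 and 0.072 SD at r = 0.3, 0.5 and 0.7, falling below 0.06 at r of about 0.8.

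The cost is a short recalculation and a few sentences in one section, with enrolment, design and models unchanged. The stated sensitivity for H2 and H3 will look less favourable than it does now.
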